5.10.1.4 Adverse Events Resulting in Discontinuation of Study Drug or Study Drug Modification

A by-patient listing of AEs resulting in discontinuation of study drug will be presented. The number and percentage of patients experiencing at least 1 AE resulting in discontinuation of study drug will be summarized by MedDRA System Organ Class, High Level Term, and Preferred Term.

A by-patient listing of AEs resulting in study drug modification will be presented. The number and percentage of patients experiencing at least 1 AE resulting in study drug modification will be summarized by MedDRA System Organ Class, High Level Term, and Preferred Term.

All AEs resulting in discontinuation of study drug occurring on-study will be displayed.

5.10.1.5 Dose Limiting Toxicities

A by-patient listing of DLTs that occur during Cycle 1 of treatment will be presented by dose level for all patients enrolled during the dose-escalation portion of this study. Patients will be grouped by the dose level to which they were originally assigned, including those who receive subsequent treatment at a lower dose level.

5.10.2 Laboratory Data

For hematology parameters and chemistry parameters, shift tables of the change in National Cancer Institute Common Terminology Criteria for Adverse Events (NCI CTCAE) from baseline to the worst postbaseline CTCAE grade will be generated. If necessary, graphical displays will be used to show changes in laboratory measures over time for each individual patient by the line graphs of individual tests over time for each patient

In addition, the lines of mean estimates over time by linear mixed model may be graphed for a selected list of test parameters.

MLN9708
Study C16007 Statistical Analysis Plan

Panel	Test	CTCAE Shift Table	Line Graphs
Chemistry	Albumin	X	X
	ALT	X	X
	AST	X	X
	Alkaline Phosphatase	X	X
	Creatinine	X	X
	Bilirubin	X	X
	Phosphate	X	X
	Uric Acid	X	
	Calcium	X	X
	Magnesium	X	X
	Potassium	X	
Hematology	Sodium	X	
	Glucose	X	
	Platelet	X	X
	Hematocrit		
	Hemoglobin	X	X
Cardiac markers	White Blood Cells (WBC)	X	
	Lymphocytes	X	X
	Neutrophils (ANC)	X	X
	NT-ProBNP		X
24 hours urine collection	BNP		X
	Troponin T		X
	Total protein		X
	Creatinine Clearance		X

In addition, the coagulation parameters and urinalysis parameters will be presented in by-patient listings and are listed below:

- Coagulation (from patients in the tumor pharmacodynamic expansion cohort and in the MTD disease expansion cohort to undergo tumor biopsy): prothrombin time (PT), partial thromboplastin time (PTT), and international normalized ratio (INR).
- Urinalysis: appearance and color, blood, pH, nitrite, specific gravity, urobilinogen, protein, glucose, ketones, leukocyte esterase, and bilirubin
- Hormones: thyrotropin (TSH) and cortisol
- β 2-microglobulin

For the purposes of summarization in both the tables and listings, all laboratory values will be converted to standardized units. If a lab value is reported using a nonnumeric qualifier (eg, less than (<) a certain value, or greater than (>) a certain value), the given numeric value will be used in the summary statistics, ignoring the nonnumeric qualifier.

If a patient has repeated laboratory values for a given time point, the value from the last evaluation will be used.

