The estimated safe starting dose of MLN9708 will be selected from the dose-escalation portion of

the C16004 study, a phase 1 study of weekly dosing in patients with relapsed and refractory multiple myeloma. The starting dose will be at least 1 dose level below the C16004 MTD (if it has been reached by the time this study starts) and, if not, then a dose level completed without documented dose-limiting toxicity (DLT).

DLTs will be assessed in Cycle 1 only. In the context of emerging clinical data of single-agent MLN9708, dose-escalation of MLN9708 will continue until the MTD has been identified or a maximum planned dose (MPD) is determined to be safe.

Once the MTD/RP2D has been established, 2 expansion cohorts of patients with relapsed or refractory amyloidosis, including approximately 10 proteasome inhibitor-naïve patients and approximately 16 proteasome inhibitor-exposed patients, will be treated at the MTD/RP2D to more fully characterize the safety, tolerability, and efficacy of MLN9708, and the PK and pharmacodynamics of MLN9708 in this patient population. As many as 30 patients will be enrolled in the dose-escalation portion of the study, and as many as 20 additional patients (26 in total, including 6 patients from the dose-escalation portion) will be enrolled in the expansion cohorts.

Toxicity will be evaluated according to the investigators' documentation of adverse events (AEs) using the National Cancer Institute Common Terminology Criteria for Adverse Events, version 4.03. AEs will be assessed, and laboratory values, vital signs, and ECGs will be obtained to evaluate the safety and tolerability of MLN9708.

Patients will be evaluated at scheduled visits over 4 study periods: Screening, Treatment, End of Treatment (EOT), and Follow-up (progression-free and overall survival). Patients will discontinue treatment if they experience PD or unacceptable toxicity. The maximum duration of treatment with either single-agent MLN9708 or MLN9708 plus dexamethasone, however, will be 12 cycles unless after discussion between the investigator and the sponsor, it is determined that a patient would derive benefit from continued therapy beyond 12 cycles.

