- g 24-hour Holter monitor, to be performed at screening, and at any time the physician believes it is medically appropriate.
- h A full physical exam will occur every 3 cycles. Symptom-directed assessments will be conducted per standard clinical practice.
- i Should occur every 3 cycles.
- j A serum pregnancy test will be performed for women of childbearing potential during screening and predose on Cycle 1, Day 1. The serum pregnancy test may be collected up to 3 days before dosing. The results must be available and negative before the first dose of MLN9708 is administered.
- k Hematology and chemistry panels may be collected up to 3 days prior to dosing. Criteria for retreatment are provided in Section 6.5.2. After 24 cycles on treatment, hematology and chemistry laboratory evaluations may be done to monitor the patient according to standard clinical practice per the treating physician.
- l Repeat as clinically indicated by change in serum creatinine. Creatinine clearance will be calculated based on a 24-hour urine collection at screening. eGFR will be calculated according to the equations in Section 15.1. 24-hour urine for protein is required to assess amyloid renal involvement/ response.
- m If abnormal, a diagnostic work up should be performed and the patient treated and stabilized before administering MLN9708. PT/INR and PTT may be repeated during the treatment period at the discretion of the investigator if bleeding occurs or as clinically indicated.
- n Only for patients in the extension cohort after every cycle.
- o Repeat every treatment cycle, at the EOT visit, and every 6 weeks during the PFS follow-up period.
- p CCI
- q Bone marrow biopsy and aspirate should be repeated at the discretion of the investigator as clinically indicated and if response is documented by other parameters, and at EOT. Immunohistochemistry of dominant clonal plasma cells is recommended.
- r To be performed at screening and at any time the physician believes there are symptoms or signs that suggest increased or new bone lesions. Plain films of symptomatic sites for signs or symptoms of new bone lesions may be obtained instead of a full skeletal survey. A PET-CT may be done at screening in

Study Procedures	Screening ^a	Treatment Period					End of Treatment ^d	Follow-up	
		CYCLES 1 -12 ^b						PFS ^e (± 1 wk)	OS ^f (± 1 wk)
	Days	Days				Every 6 weeks		Every 6 weeks	Every 12 weeks
	-28 to -1	1 ^c	8	15	Rest Period 22 to 28	Every 6 weeks		Every 12 weeks	Every 12 weeks

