6.3 Definitions of Dose-Limiting Toxicity (DLT)

6.3.1 DLT Definitions

Although DLTs may occur at any point during treatment, only DLTs occurring during Cycle 1 of treatment must influence decisions regarding dose-escalation, expansion of a dose level, or evaluation of intermediate dose levels. However, DLTs occurring in later cycles may be taken into consideration for dose-escalation decisions, at the discretion of the investigators and sponsors.

Toxicity will be evaluated according to the National Cancer Institute Common Terminology Criteria for Adverse Events (NCI CTCAE), version 4.03.⁽⁵⁸⁾ Toxicity will be evaluated

according to the National Cancer Institute Common Terminology Criteria for Adverse Events (NCI CTCAE), version 4.03. ⁽⁵⁸⁾ DLT will be defined as any of the following AEs that are considered by the investigator to be even possibly related to therapy with MLN9708:

- Any Grade 4 thrombocytopenia (platelets < 25, 000/mm³) lasting at least 7 days.
- Grade 3 thrombocytopenia with clinically significant bleeding, where clinically significant bleeding is defined as a blood loss of > 100 cc or the requirement for a RBC transfusion.
- A platelet count < 10,000/mm³.
- Any Grade 4 neutropenia (ANC < 500/mm³) lasting at least 7 days or Grade 3 febrile neutropenia with fever and/or infection where fever is defined as a temperature $\geq 38.5^{\circ}\text{C}$.
- Grade 2 peripheral neuropathy with pain or Grade 3 or greater peripheral toxicity.
- Any Grade 3 or higher nonhematologic toxicity (in particular, worsening neuropathy, diarrhea despite maximal supportive therapy, life-threatening ventricular arrhythmia or atrial arrhythmia with hemodynamic instability, fluid retention that does not resolve with 3 or 4 days of intravenous diuretic therapy and bedrest, symptomatic congestive heart failure, and hypotension); with the following exceptions: Grade 3 arthralgia/ myalgia and brief (< 1 week) Grade 3 fatigue.
- Grade 3 or greater nausea and/or emesis despite the use of optimal anti-emetic prophylaxis. Optimal anti-emetic prophylaxis is defined as an anti-emetic regimen than employs 5-HT₃ antagonist given according to standard practice.
- A delay of more than 2 weeks in the initiation of Cycle 2 of treatment because of a lack of adequate recovery of MLN9708-related hematological or nonhematologic toxicities.

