8. STATISTICAL AND QUANTITATIVE ANALYSES

8.1 Statistical Methods

8.1.1 Determination of Sample Size

A 3 + 3 dose-escalation scheme will be conducted, with 3 to 6 DLT-evaluable patients evaluated at each dose level. It is expected that as many as 30 patients will be enrolled in the dose-escalation part of this study.

Once the MTD/R2PD has been established, the following 2 expansion cohorts will be treated at the MTD or RP2D.

1. Proteasome inhibitor-naive expansion cohort including approximately 8 organ response-evaluable patients. There will be approximately 83% probability of observing at least 2 patients with organ responses among 8 patients based on the binomial probability calculation if the overall organ response rate is 35% for this population. Approximately 10 patients will be enrolled to obtain 8 response-evaluable patients.
2. Proteasome inhibitor-exposed expansion cohort including approximately 14 organ response-evaluable patients. There will be approximately 80% probability of observing at least 2 patients with organ responses among 14 patients based on the binomial probability calculation if the overall organ response rate is 20% for this population. Approximately 16 patients will be enrolled to obtain 14 organ response-evaluable patients.

Because approximately 6 patients in the dose-escalation part of the study will be included in the expansion cohorts, approximately 20 patients will be enrolled in the expansion part of this study.

Overall, as many as 50 patients will be enrolled in this study.

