5.2 Randomization and Stratification

No randomization or stratification will be performed in this study. Patients will be enrolled in successive dose cohorts during dose escalation. For the MTD disease expansion cohorts, patients will be enrolled in 1 of 2 expansion cohorts based on whether they have received a proteasome inhibitor-containing therapy.

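### SAP 5.10.2 restricts the coagulation listing to cohorts that do not match this trial's design, so as written it covers between 0 and about 26 of up to 50 patients and conflicts with SAP 5.4.1

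*SAP*

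**What the plan says.** SAP 5.10.2 gives certain panels no table or graph, only listings: "the coagulation parameters and urinalysis parameters will be presented in by-patient listings and are listed below". The bullets beneath cover coagulation, urinalysis, hormones and β2-microglobulin. Only the first has a patient restriction: "Coagulation (from patients in the tumor pharmacodynamic expansion cohort and in the MTD disease expansion cohort to undergo tumor biopsy".

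SAP 5.2 describes the expansion part differently. It begins "For the MTD disease expansion cohorts, patients will be enrolled in 1 of 2 expansion cohorts", and the allocation criterion is prior treatment: "patients will be enrolled in 1 of 2 expansion cohorts based on whether they have received a proteasome inhibitor-containing therapy". SAP 1.1 and 5.1 and protocol 4.1, 6.4 and 8.1.1 describe the same two cohorts, proteasome inhibitor-naïve and proteasome inhibitor-exposed.

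The protocol's Schedule of Events marks coagulation studies at screening with no cohort limit. Its footnote m adds: "PT/INR and PTT may be repeated during the treatment period at the discretion of the investigator if bleeding occurs or as clinically indicated". Protocol 7.5.10 includes coagulation studies in the laboratory evaluations, again for the study as a whole.

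Two general rules point the other way from the bracketed text. SAP 5.4.1 and protocol 8.1.4 both say that all available safety data go into the listings. SAP 5.10.6 adds a residual provision for listing other important collected data by patient.

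**The concern.** A reporting rule should select patients by a characteristic that exists in the trial. This one names a cohort found nowhere else in the documents, and attaches to the other cohort a biopsy condition that no visible text supports. A programmer who follows the specific instruction would produce an empty listing or one confined to the expansion cohorts. A programmer who follows the general instruction would list everyone. The SAP does not say which instruction governs.

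At stake is whether data the protocol provides for reach the study report. Clinical laboratory values are part of the primary safety endpoint in protocol 3.1. Protocol 1.2.3 reports changes in coagulation parameters in both rats and dogs at doses below those that were dose-limiting, and names bleeding among the potential risks. Protocol 6.3.1 counts "Grade 3 thrombocytopenia with clinically significant bleeding" as a DLT. A reader of the report who is reviewing a bleed would reasonably expect to find any PT, PTT or INR result taken around it.

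**Working it through.** The plan states no figure for this listing, so there is nothing to reproduce. The check sets the filter beside the design and counts the patients it covers under each available reading.

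**Inputs**
- Total enrolment, protocol 8.1.1: "Overall, as many as 50 patients will be enrolled in this study".
- Dose escalation: up to 30 patients (protocol 4.1, 4.2).
- Expansion cohorts: about 10 naïve and about 16 exposed, 10 + 16 = 26. The protocol summary and section 4.1 describe this as "26 in total, including 6 patients from the dose-escalation portion", so 26 − 6 = 20 are newly enrolled. SAP 5.4.4 also counts dose-escalation patients treated at the MTD within the expansion cohorts.
- Consistency check: 30 + 20 = 50.

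**Filter against design**

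| Element of the SAP 5.10.2 restriction | Counterpart in the documents |
|---|---|
| Tumor pharmacodynamic expansion cohort | None |
| MTD disease expansion cohort | Yes: SAP 5.2 uses this name for the two real cohorts |
| Condition of undergoing tumor biopsy | None in visible text. Bone marrow biopsy is scheduled but not tied to a cohort; skin punch biopsy is optional in case of rash |

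**Patients covered**
- (a) Literal reading, with the biopsy condition enforced: 0 of up to 50.
- (b) Biopsy condition ignored, cohort name taken as in SAP 5.2: about 26 of up to 50. Left out: 50 − 26 = 24, which equals the 30 − 6 = 24 dose-escalation patients not carried into the expansion cohorts.
- (c) General rule of SAP 5.4.1 and protocol 8.1.4 allowed to override: up to 50 of 50.

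Readings (a) and (b) apply the restriction; reading (c) sets it aside.

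**Who is left out under (b).** These are the dose-escalation patients not treated at the expansion dose, including any treated above it. SAP 2.2 draws the DLT-evaluable population from dose escalation, and protocol 6.10 says thrombocytopenia has been seen mainly at the higher doses tested.

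**Unscheduled repeats.** SAP 5.4.3 assigns data to the scheduled visit at which they were collected. On-treatment PT, PTT and INR have no scheduled visit, and the SAP has no explicit rule for unscheduled values. Removing the cohort restriction alone would therefore not make it plain that repeats are listed.

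**The case against.** The strongest reply is that the bracket is stale text with no real effect. SAP 5.4.1, protocol 8.1.4 and SAP 5.10.6 each support listing the data. SAP section 6, which records departures from the protocol, does not mention restricting coagulation results. Bleeds are captured as AEs or SAEs, Cycle 1 DLTs are listed, and platelets have a shift table and line graphs. A coagulation abnormality that leads to intervention or a treatment change, or is judged clinically significant, becomes an AE under protocol 10.1.2.

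Much of this stands, and it limits the point. A reader might infer that coagulation results would be reported for nobody. The documents do not support that as a fact. The general rules point to full listing, SAP 5.2 gives part of the restriction a real referent, and the tumor biomarker sections and the screening marrow footnote are redacted, so a tumor-sampling procedure cannot be excluded. A reader might also infer that the loss would fall mainly on patients who bled. That is not supported either: repeats are discretionary, may be done for any clinical indication, and no frequency is given. Nor do PT, PTT or INR enter the bleeding DLT, which turns on platelet grade with blood loss above 100 cc or a red cell transfusion.

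The reply does not remove the conflict. A specific instruction for one panel is commonly followed over a general one, and the silence of section 6 can equally be read as an undeclared departure from protocol 8.1.4. SAP 5.10.6 depends on someone judging the results important. AE reporting is not equivalent, because a normal INR during a bleed is informative but would never be recorded as an AE.

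**Conclusion.** The restriction in SAP 5.10.2 is wrong as written and conflicts with SAP 5.4.1, protocol 8.1.4 and the protocol's all-patient coagulation schedule. If applied, it covers 0 to about 26 of up to 50 patients, and up to 24 dose-escalation patients are left out even on the more generous of those two readings. If the general rule prevails, nobody is left out.

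The figures assume planned maximum enrolment and the approximate cohort sizes in the documents. The zero rests on visible text only. The wording looks carried over from another plan, since SAP 5.4.4 likewise refers to a modified accelerated titration design although the trial uses 3 + 3, but that is an inference. The case report form was not available, so whether unscheduled coagulation results are captured is unknown.

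Severity is low. One descriptive listing is affected; no MTD rule, DLT definition, efficacy endpoint or summary table changes.

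**What to change.** In SAP 5.10.2, delete the bracketed cohort restriction on the coagulation bullet. Replace it with a statement that PT, PTT and INR, from both scheduled and unscheduled assessments, are listed for all patients in the Safety population. This brings the section into line with SAP 5.4.1 and protocol 8.1.4.

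The cost is about one line of SAP text. It asks for no new assessments and changes no dose or clinical rule. The sponsor should confirm that the case report form captures unscheduled coagulation results.

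Flagging values taken around a bleeding AE would help a reader but is optional. It would need a defined time window and a link between AE and laboratory records, so it costs more than the core change.

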6.6.1 MLN9708 Dose Adjustments for Hematologic Toxicity

Dosage adjustments for hematologic toxicity are outlined in [Table 6-2](#).

Table 6-2 MLN9708 Dose Adjustments for Hematologic Toxicities

Criteria	Action
Within-Cycle Dose Modifications	
If platelet count $\leq 30 \times 10^9/L$ or ANC $\leq 0.75 \times 10^9/L$ on a MLN9708 dosing day (other than Day 1)	MLN9708 dose should be withheld. Complete blood count (CBC) with differential should be repeated at least every other day until the ANC and/or platelet counts have exceeded the prespecified values (see Section 6.5.2.1) on at least 2 occasions. In the event CBC cannot be repeated at least every other day, dose modifications should be made in consultation with sponsor. Upon recovery, MLN9708 may be reinitiated with 1 dose level reduction or by 33% if the patient is receiving the first dose level.
Dose Modifications for Subsequent Treatment Cycles	
Delay of > 2 weeks in the start of a subsequent cycle due to lack of toxicity recovery as defined in Section 6.5.2 :	
 - Hold MLN9708 until resolution as per criteria Section 6.5.2. - Reduce MLN9708 1 dose level or 33% if the patient is receiving the first dose level. - The maximum delay before treatment should be discontinued (except in the case of investigator determined clinical benefit and discussion with the Millennium clinician) will be 3 weeks.
Dose Modifications for Subsequent Treatment Cycles	
All hematologic toxicities	For hematologic toxicity that occurs during a cycle but recover in time for the start of the next cycle, a dose level reduction will be made either based on within-cycle or for

Table 6-2 MLN9708 Dose Adjustments for Hematologic Toxicities

Criteria	Action
	subsequent cycle criteria, but not for both from the same cycle.

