7.5.10 Clinical Laboratory Evaluations

Handling of clinical laboratory samples will be outlined in the Study Manual. Decisions regarding eligibility for this study may be made using local laboratory determinations. For dosing decisions, local hematology and chemistry laboratory results may be used.

Hematology and chemistry panels may be collected up to 72 hours prior to dosing. Criteria for retreatment are provided in Section 6.6.

Clinical Chemistry and Hematology

Blood samples for analysis of the following clinical chemistry and hematological parameters will be obtained as specified in the [Schedule of Events](#). After 24 cycles on treatment, hematology and chemistry laboratory evaluations may be done to monitor the patient according to standard clinical practice per the treating physician.

Hematology

- Hemoglobin
- Hematocrit
- Platelet count
- WBC count with differential

Serum Chemistry

- Blood urea nitrogen (BUN)
- Creatinine
- Total bilirubin
- Uric acid
- Lactate dehydrogenase
- Alkaline phosphatase
- AST
- ALT
- Albumin
- Glucose
- Sodium
- Potassium
- Chloride
- CO₂
- Magnesium
- Calcium
- Phosphate

Urinalysis

- Appearance and color
- pH
- Specific gravity
- Protein
- Ketones
- Bilirubin
- Blood
- Nitrite
- Urobilinogen
- Glucose
- Leukocytes
- Microscopic assessment

24-Hour Urine Collection

- Total protein
- Creatinine

Coagulation Studies

- Prothrombin time and international normalized ratio
- Activated partial thromboplastin time

Hormones

- Thyrotropin (TSH)
- Cortisol

Other

- Cardiac Markers:
BNP, NT-ProBNP, and troponin T or I
- β 2-microglobulin

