Shift tables for laboratory parameters will be generated based on changes in NCI CTCAE Grade from baseline to the worst post baseline value. Graphical displays of key safety parameters, such as scatter plots of baseline versus worst post baseline values, may be used to understand the MLN9708 safety profile.

All concomitant medications collected from screening through the study period will be classified to preferred terms according to the World Health Organization (WHO) drug dictionary.

Additional safety analyses may be performed to most clearly enumerate rates of toxicities and to further define the safety profile of MLN9708.

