5.4 Data Handling

5.4.1 Methods for Handling Missing Data

Decisions regarding eligibility for this study may be made using local laboratory determinations in the dose-escalation segment of this study. For dosing decisions, local hematology and chemistry laboratory results may be used.

All available efficacy and safety data will be included in data listings. For summary tables, laboratory test results from the central laboratory will be used when they are available. Laboratory test results from local laboratories will be used only when no central laboratory test results exist at the same scheduled sample collection time point and when the local laboratory results support an adverse event (AE), dose modification, or other medical decision.

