5.4.3 Windowing of Visits

All data will be categorized based on the scheduled visit at which they were collected. These visit designators are predefined values that appear as part of the visit tab in the electronic case report form (eCRF).

Refer to protocol Section 7.4.14 for details about the PK and pharmacodynamic sample collection windows.

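### Minor: the SAP keeps only the last of repeated laboratory values at a time point and does not exempt the shift tables, which are defined by the worst postbaseline grade

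*SAP*

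**What the plan says.** SAP 5.10.2 plans shift tables of the change in CTCAE grade "from baseline to the worst postbaseline CTCAE grade will be generated". Protocol 8.1.8 plans the same display: "Shift tables for laboratory parameters will be generated based on changes in NCI CTCAE Grade from baseline to the worst post baseline value". The SAP table marks 18 tests for it (13 chemistry, 5 hematology).

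At its end, SAP 5.10.2 adds a rule for repeats: "If a patient has repeated laboratory values for a given time point, the value from the last evaluation will be used". It does not say which displays the rule governs.

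Three other provisions bear on how the rule works:

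- SAP 5.4.3 assigns results to visits: "All data will be categorized based on the scheduled visit at which they were collected". It gives no rule for unscheduled draws.
- SAP 5.4.1 prefers central results in summary tables. Local results "will be used only when no central laboratory test results exist at the same scheduled sample collection time point". A second condition must hold too: the local value has to bear on an adverse event, a change of dose or some other clinical decision. Protocol 7.5.10 adds: "For dosing decisions, local hematology and chemistry laboratory results may be used".
- Protocol 6.6.1, Table 6-2, says that after a dose is withheld for low counts, the blood count "should be repeated at least every other day until the ANC and/or platelet counts have exceeded the prespecified values". Two such counts are needed as a minimum.

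**The concern.** A worst-grade table needs every postbaseline value, while a last-value rule throws some away. The two instructions stand in the same section with nothing to reconcile them. The shift table is the only laboratory summary table that SAP 5.10.2 specifies (the rest are graphs and listings), so a programmer working from that text has no reason to exempt it.

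Clinical laboratory values are among the primary endpoints (protocol 3.1), and the shift tables are their main graded summary. If a worse value is lost, the shift table can show a milder worst grade than the adverse event table in the same report. An abnormal value that prompts no action and is not judged clinically significant is not an adverse event (protocol 10.1.2). For such values the shift table is the only graded summary.

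**Working it through.** The plan gives no figure to reproduce. The check reads the rules together and applies them to assumed platelet counts (× 10^9/L).

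**Inputs**
- Grade 4 platelets: below 25 (protocol 6.3.1).
- Within-cycle hold: platelets ≤ 30 or ANC ≤ 0.75 on a dosing day other than Day 1 (Table 6-2).
- Recovery values: platelets 75, ANC 1.0 (protocol 6.5.2.1).
- Predose window: 3 days (Schedule of Events, footnote k).

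**Direction**
- Definition of the table: worst grade = maximum grade over all postbaseline values.
- With the last-value rule: worst grade = maximum over time points of the grade of the last value at each.
- The second maximum runs over a subset of the first, so it can be equal or lower, never higher. It is equal when the last repeat is the worst, or when another time point carries a grade at least as severe.

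**Case A: two draws in one predose window (assumed)**
- 22 then 28: all values, min(22, 28) = 22 < 25, Grade 4. Last value, 28, not Grade 4.
- 28 then 22: last value = 22 = min, so nothing is lost.

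**Case B: recovery counts after a Day 8 hold (assumed)**
- At the minimum every-other-day frequency, repeats fall on Days 10, 12 and 14, that is, 3 before the Day 15 draw.
- Assumed series: Day 8 = 22, Day 10 = 40, Day 12 = 80, Day 14 = 95, Day 15 = 90.
- Repeats given their own designators: min(22, 40, 80, 95, 90) = 22, Grade 4. Nothing is lost.
- Repeats filed under Day 8, last kept: Day 8 becomes 95, and min(95, 90) = 90, not Grade 4.
- For a patient who recovers, the last repeat lies well above the hold limit: by more than 75/30 = 2.5 times for platelets and more than 1.0/0.75 = 1.33 times for ANC. In this setting the last value is systematically a good one.

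**Interaction with SAP 5.4.1 in Case B, repeats filed under Day 8**
- Day 8 has a central result of 22 and the repeats are local: 5.4.1 excludes the repeats because a central result exists at that time point. Day 8 stays 22, min(22, 90) = 22, and Grade 4 is kept.
- Day 8 has no central result and the local values support dosing decisions: all are admitted, the last-value rule leaves 95, and Grade 4 is lost.
- All results are central: the last-value rule leaves 95, and Grade 4 is lost.
- The SAP does not state in which order the two rules apply.

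**The case against.** The best defence is ordinary reading. The repeat rule concerns a given time point, the shift table is not a time-point display, and a specific definition normally prevails over a general one. The rule also has an obvious use elsewhere: the line graphs and model-based mean plots in SAP 5.10.2, and the descriptive statistics by scheduled measurement in protocol 8.1.8. This may well be what the sponsor intends. The SAP does not say so, however, and one sentence would settle it.

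The filing objection largely stands. A Day 10 count was not collected at the Day 8 visit, and the eCRF visit labels cannot be seen. Case B is therefore conditional, and SAP 5.4.1 may cancel it.

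The safety net is real. Values that cause a hold qualify as adverse events (protocol 10.1.2). Grade 3 and Grade 4 events, and events leading to drug modification, are tabulated (SAP 5.10.1.1, 5.10.1.4). All values stay in listings (SAP 5.4.1).

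A reader might infer more than the documents support:
- That the central-over-local rule is a second error reaching all 18 tests. Prespecifying one laboratory source is a defensible choice, and taking the worse of two assays would push grades upward. Assumed values of 24 (local) and 26 (central) straddle the Grade 4 limit, but this shows only a small difference between laboratories.
- That at least 2 of the Day 10, 12 and 14 counts must be recovered for dosing on Day 15. The Day 15 draw can be one of the 2 occasions, and Table 6-2 also allows for counts that cannot be repeated that often.
- That cycle-start delays lose values in the same way. A draw that fails and causes a 1-week delay falls outside the 3-day window, so it is not a valid Day 1 sample for the cycle that later starts.

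**Conclusion.** The point holds as a minor inconsistency. As written, the last-value rule conflicts with the definition of the shift tables, and any effect is in one direction: unchanged or milder. It requires repeats that share a time point, an earlier value with a worse grade than the last, and no equally severe grade at another time point. How often this happens depends on visit labelling and on how often central and local results coexist, neither of which the documents give. The size is therefore not estimable and may be nil. The platelet values above are assumptions that show the mechanism, not its frequency.

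A reader might infer that dose finding is at risk. The documents do not support this: MTD rests on DLTs, and RP2D on DLTs, adverse events and efficacy, none of which pass through the shift tables. Adverse event tables and data listings are likewise unaffected.

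**What to change.** State in SAP 5.10.2 that the worst postbaseline grade is taken over all eligible postbaseline results, whether scheduled, repeat or unscheduled, and that the last-value rule applies only to by-visit summaries and plots over time.

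The source preference in SAP 5.4.1 can stay. At most, clarify whether a local result that drove a dose modification counts toward the worst grade when a central result exists at the same time point.

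The cost is one SAP sentence and a small programming change. Displayed laboratory grades may look slightly less favourable. If local results are to count alongside central ones, local normal ranges must also be available for grading.
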